Protocol Clinical Trial

Study synopsis

Study overview	
Title of clinical trial	Low grade inflammation in childhood obesity : an independent risk factor for endothelial dysfunction ?
Sponsor name	University Hospital of Brussels
Principal Investigator	prof. dr. [name] / [name]
Medical condition or disease under investigation	Obesity and overweight, cardiovascular risk factors
Purpose of clinical trial	To assess whether low grade inflammation in childhood obesity contributes to endothelial dysfunction
Primary objective	To investigate if the reactive hyperemia index by peripheral arterial tonometry is higher in adolescents with a history of childhood obesity and presenting a low grade inflammation in comparison with those without low grade inflammation (hSCRP < or > 1 mg/L)
Secondary objective (s)	To analyze the changes in hCRP and adiposity in obese children and adolescents after 5 to 10 years
Trial Design	Observational cohort study
Endpoints	RH-PAT scores, measured by peripheral artery tonometry . hSCRP, measured by automated immunoturbidometry BMI z-score and % body fat by skinfold thickness
Sample Size	54 (α= 0,05 – power 80%)
Summary of eligibility criteria	Overweight and obese adolescents, aged 12 to 21 years, with a known level of hs-CRP at initial evaluation for metabolic syndrome
Maximum duration of intervention	Single visit
Version and date of final protocol	Protocol version 1, date 18/08/2018
Version and date of protocol amendments	Not applicable

Study Schedule

Administrative information

1. Sponsor

The study is sponsored by the division of pediatric endocrinology of the University Hospital of Brussels (UZ Brussel).

2. (Principal) Investigator(s)

Prof. dr. [name]

Dr. [name]

[name]. [name]

[name] [name]

[name]

3. Departments involved

Department of Pediatrics

Division of Pediatric Endocrinology

University Hospital of Brussels

[name]

Ethical and regulatory information

1. Study registration

The study is registered at ClinicalTrials.gov and has a unique number: ####.

2. Study type

The study is an observational cohort study

3. Competent Ethics Committee

Central Ethics Committee:

Ethical Committee University Hospital of Brussels

[contact]

Email: [contact]

4. Ethical conduct of the study

The trial will be conducted in compliance with the principles of the Declaration of Helsinki (current version), the principles of Good Clinical Practice (GCP) and in accordance with all

applicable regulatory requirements. This protocol and related documents will be submitted for review to Ethics Committee before start of the trial.

5. Declaration of conflict of interest

The investigators of this study declare that they don't have any competing interests.

6. Patient information and informed consent

The study will be conducted only after obtaining a prior informed consent of the legal representatives of the children and obtaining an assent of the children according to their age and maturity. The legal representatives of the children will sign an informed consent form and the assent of the children will be noted in the corresponding file. The informed consent form and the assent will be reviewed by the Ethics Committee prior to the start of recruitment.

7. Participant privacy and confidentiality

The investigators shall treat all information and data relating to the study disclosed to Participating Site and/or Investigator in this Study as confidential and shall not disclose such information to any third parties or use such information for any purpose other than the performance of the study. The collection, processing and disclosure of personal data, such as patient health and medical information is subject to compliance with applicable personal data protection and the processing of personal data (Directive 95/46/EC and Belgian law of December 8, 1992 on the Protection of the Privacy in relation to the Processing of Personal Data) as well as the General Data Protection of April 2018.

The data will be coded. There continues to be a link between the data and the individual who provided it. The research team is obligated to protect the data from disclosure outside the research according to the terms of the research protocol and the informed consent document. The subject's name or other identifiers are stored separately from their research data and replaced with a unique code to create a new identity for the subject.

8. Early termination of the study

Not applicable.

9. Protocol amendments

Changes to the study protocol will be submitted to the Ethics Committee and will not be performed before obtaining an approval.

10. Reward

Participant will not receive a compensation for their participation in the study. If needed, an absence certificate will be provided for the participant and/or the accompanying adult at the time of the study visit.

Background and rationale

Obesity and overweight have become an important health burden in children and adolescents, with 19% of all children between 5 and 18 years being either obese or overweight in Belgium(1,2). Obesity and especially visceral adiposity early in life may contribute to the development of cardiovascular disease at older age, as it shows tracking into adulthood and is associated with cardiovascular risk

factors such as dyslipidemia, insulin resistance, arterial hypertension and low grade inflammation, in a variable percentage (4) (5)

Low grade inflammation, as assessed by hSCRP, was found to be present in 20.6 % and 19.8 % of overweight children and adolescents (6). In adults, hSCRP levels between 1 and 3 mg/L and above 3 mg/L are considered coronary disease risk factors (7).

Endothelial dysfunction, known to precede the formation of atherosclerotic plaque, can be assessed in a non-invasive manner in children by peripheral artery tonometry. (8) Only few studies have been performed in obese children with this bed-side technique, showing either normal or a disturbed function, reflected by a lower reactive hyperemia index (9, 10,11) The association with low grade inflammation however was assessed in only one study. We hypothesize that in adolescents and young adults with a history of childhood obesity a more disturbed endothelial function will be present in those with and /or current elevated hSCRP value.

Study Objectives

To investigate whether obese and overweight adolescents with an elevated hs-CRP are more at risk for the development of endothelial dysfunction assessed peripheral artery tonometry, compared to those with a normal hs-CRP at their initial evaluation for obesity-associated metabolic syndrome

To assess the degree of endothelial dysfunction, assessed by the reactive hyperemia index by peripheral artery tonometry in adolescents and young adults with a history of childhood obesity in relation to their current hs CRP value

To investigate the changes in hs-CRP and adiposity in adolescence and young adulthood of initially obese children and adolescents with either normal or elevated hs-CRP levels

Study outcomes

1. Primary outcome

Reactive hyperemia index (RHI) measured by the EndoPAT device

2. Secondary outcome

hs CRP value , BMI z-score and body fat percentage assessed by skinfold thickness

Study design

1. Overall design

This is an observational cohort study

2. Randomization/blinding procedure.

Not applicable.

3. Statistical methodology

The statistical analysis will be done with the SPSS software.

The difference in THI index between the population with and without low grade inflammation will be evaluated by the Mann Whitney U test and Multivariate analysis of variance, taking current hCRP, age, BMI z-score, and systolic blood pressure into account. The change in hS

CRP in the population with and without low grade inflammation will be analyzed by the Kruskall Wallace test.

The power calculation was done at clincalc.com/stats/samplesize software. Assuming a mean RHI score of 1.51 in overweight children with a standard deviation of 0.2 (9), assuming an equal distribution between the study groups (elevated vs. normal hs-CRP), we have a power of 0.80 to demonstrate a difference of 20 % between the two groups with 27 patients enrolled in each group.

Study population

1. Recruitment

Eligible candidates will be recruited within the children with overweight and obesity having a metabolic risk evaluation before treatment in the period 2006 and 2010 at the pediatric clinic of the UZ Brussel. In total 60 participants will be investigated. Firstly, 30 participating patients with initially elevated hsCRP will be selected at random (following the date of their initial investigation) and afterwards matched for age, BMI z-score, and blood pressure with the same number of patients without initially elevated hCRP values

2. Recruitment procedure

Eligible candidates, or their parents if underage, will be personally contacted by telephone and/or e-mail by their initial pediatric endocrinologist and will be invited to partake in the study. All written information about the study will be provided beforehand.

3. Eligibility criteria

➤ Inclusion Criteria:

- Age 12-21 years at the moment of evaluation
- BMI > 1.3 SDS at the initial evaluation
- Hs-CRP available at initial evaluation

➤ Exclusion Criteria

- Acute or chronic Infection at the time of the study visit

Be or have been a smoker of tobacco

Study intervention

1. Study overview

A single visit is planned. During this visit a standard questionnaire on current health status, life style will be filled in a selfscore of pubertal development using standardized pictures will be done. Standard anthropometrics and blood-pressure measurements , a blooddrawn for hSCRP and a peripheral artery tonometry will be performed.

2. Identification of intervention

➤ Anthropometry:

Anthropometric measurement sites are defined according to the international standards. (10)

- Weight will be measured using a calibrated digital scale (SECA, Hamburg, Germany) and will be rounded up to the nearest 0,05 kg. Participants will be wearing light clothing (underwear).
- Standing height will be measured using a stadiometer with a movable headboard and vertical backboard and will be rounded up to the nearest 0,1 cm.
- Waist circumference will be measured in the middle of the lowest rib (10th rib) and the iliac crest at the end of a normal expiration. The girths will be measured with a flexible Lufkin steel anthropometric tape (Lufkin W606PM).
- Tricipital and subscapular skinfold thickness will be measured by a Harpenden caliper using the Slaughter guidelines.
- The BMI z-score will be calculated using the Vlaamse groeistudie 2004 references
- The Slaughter formula will be used to calculate the body fat percentage.

➤ Blood pressure (mean of 3 measurements)

Blood pressure will be measured using an oscillometric, electronic device (Mindray). The blood pressure will be measured 3 times; the first measurement will not be taken into account and the mean of the second and third measurement will be calculated.

➤ Peripheral arterial tonometry

The pulse wave amplitude will be measured by a commercial finger plethysmograph EndoPAT, Itamar Medical Ltd, Caesarea, Isreal.)

Briefly explained, both index fingers of the patient are placed in the pneumatic probes. First the device performs 5 minutes of baseline measurement and thereafter a blood pressure cuff occludes the arterial flow of the arm for 5 minutes. After a rapid deflation of the cuff a

reactive hyperemia takes place which is a measure for the arterial endothelial function. There is a concomitant software package which calculates the Reactive Hyperemia Index (RHI) and peak dilatation.

Participants will be asked not to engage in strenuous sport activities the 24 hours preceding the test. (12)

hS-CRP

Will be measured at the Chemical Chemistry Laboratory of the UZ Brussel using by immunoturbimetry by the Vitros 4600 / Ortho Clinical Diagnostics analyzer.

Safety

1. Insurance

All damage or injuries resulting from the study participation will be covered by the no fault insurance available at Ethias through the University Hospital of Brussels.

2. Anticipated possible adverse events

The peripheral arterial tonometry can cause a tingling feeling in the occluded arm that will disappear after deflation of the cuff.

Drawing blood may lead to discomfort, pain or a hematoma at the puncture site and syncope.

Quality assurance

EndoPAT device measurements will be done by the same person after training by the technicians. Calibrated instrumented will be used and blood will be drawn according to standard procedures in the University Hospital of Brussel (UZ Brussel). The CRP analysis has a CV of 4.8 % for 1.03 mg/L value.

Privacy policy

The medical file data will be collected after agreement of the responsible treating paediatric endocrinologist. The questionnaire data and medical file data will be merged into an Excel document, which will be protected by a password. All the obtained data will be handled in a confidential way. All names, birth dates and residence data will be erased from the final datafile, which will be stored on a protected server of the UZ Brussel by Prof dr [name], who is the responsible for the data collection and storage. Collected data will be stored for 5 years. The Data Protection Officer of the UZ Brussel ([name] ([contact]) is responsible for further information on data protection. Participants will be informed about the DPO and their right to correct or withdraw collected data.

Publication policy

All publication rights of unprocessed and processed data belong to the investigators.

References

- 2.Wetenschappelijk Instituut Volksgezondheid. Gezondheidsenquête 2013.
- 4.Park MK. Park's pediatric cardiology – sixth edition. Philadelphia: Elsevier Saunders; 2014. 33, Dyslipedemia and other cardiovascular risk factors; p. 520-552.
5. Franks PW et. al. Childhood obesity, other cardiovascular risk factors and premature death. *N Engl J Med.* 2010;362(6):485-93.
6. Visser M et al. Low-grade systemic inflammation in overweight children. *Pediatrics.* 2001 Jan;107(1):E13.

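### Blinding is declared not applicable, although the person who measures endothelial function could be kept unaware of the hs-CRP group at little cost

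*Combined protocol and SAP*

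**What the plan says.** In the protocol's Study design section, item 1 reads "This is an observational cohort study". Item 2, headed "Randomization/blinding procedure", is answered with a single entry, not applicable, which covers both halves of the heading.

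The passages that bear on masking are these:

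- **Grouping.** Study population, Recruitment: "Firstly, 30 participating patients with initially elevated hsCRP will be selected at random", and the same number of patients without initially elevated values are then matched to them.
- **Contact.** Recruitment procedure: candidates are "personally contacted by telephone and/or e-mail by their initial pediatric endocrinologist".
- **Primary outcome.** Study outcomes: "Reactive hyperemia index (RHI) measured by the EndoPAT device".
- **Operator.** Quality assurance: "EndoPAT device measurements will be done by the same person after training by the technicians".
- **Derivation of the index.** Study intervention, Peripheral arterial tonometry: "There is a concomitant software package which calculates the Reactive Hyperemia Index (RHI) and peak dilatation".
- **Skinfolds, the basis of body fat percentage (a secondary outcome).** Study intervention, Anthropometry: "Tricipital and subscapular skinfold thickness will be measured by a Harpenden caliper using the Slaughter guidelines". Who takes them is not stated.
- **Coding.** The section on participant privacy and confidentiality replaces identifiers by a unique code and keeps a link to the individual. It presents this as data protection and does not mention masking.

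**The concern.** Randomization and masking of the assessor are separate safeguards. The first has no place in this design. The second does: the exposure is a laboratory value already on file, the outcome is measured years later, and the measurer does not need the exposure to do the job.

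The Background states a directional hypothesis, namely more disturbed endothelial function where hs-CRP is or was elevated. Someone who knew a participant's group would therefore have an expectation about the result. If that expectation affected how tests were carried out or which recordings were kept, the effect would fall between the two groups being compared, and neither a larger sample nor the planned covariates would remove it. Having one operator removes differences between operators, but it does not protect against a difference in how that operator handles the two groups.

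**Working it through.** The plan gives no figure for measurement bias, so there is none to reproduce. The check has two parts.

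**1. What the text establishes**

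| Question | What the documents say |
|---|---|
| Is group membership fixed before the visit? | Yes. Selection and matching are by initial hs-CRP. |
| Does one person do all EndoPAT tests? | Yes. |
| Is that person kept unaware of the group? | Not stated; blinding is declared not applicable. |
| Does that person know the group? | Not stated. |
| Does that person select or contact participants? | Not stated. Contact is by the initial pediatric endocrinologist. |
| Is the index read subjectively? | No. Software calculates it. |
| Who may repeat or reject a recording, and by what rule? | Not stated. |
| Who takes the skinfolds? | Not stated. The single-operator sentence covers EndoPAT only. |
| Is current hs-CRP known during the test? | Not stated. Blood is drawn at the same visit and analysed in the hospital laboratory; the order of procedures is not given. |

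The text thus shows that a feasible safeguard is ruled out, not that measurement is unmasked in practice.

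**2. How sensitive the primary comparison is to a systematic shift (illustration)**

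Inputs: SD 0.2 and mean RHI 1.51 (Statistical methodology); 30 per group (Recruitment, 60 in total); two-sided alpha 0.05 (alpha is from the synopsis, two-sidedness is assumed). The shifts are assumed: 0.02, 0.05 and 0.075 RHI units, or about 1%, 3% and 5% of 1.51.

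Standard error of the difference: SE = SD × √(2/n) = 0.2 × √(2/30) = 0.0516.

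With no true difference and a shift b between groups, the t statistic on 30 + 30 − 2 = 58 degrees of freedom has noncentrality b/SE. The false-positive rate is the probability that it exceeds the two-sided 5% critical value in either direction.

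| Assumed shift b | b/SE | False-positive rate, 30 per group | Same, 27 per group |
|---|---|---|---|
| 0 | 0 | 0.050 | 0.050 |
| 0.02 | 0.39 | 0.067 | 0.065 |
| 0.05 | 0.97 | 0.159 | 0.147 |
| 0.075 | 1.45 | 0.298 | 0.272 |

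The last column uses the 27 per group of the power calculation; the picture is the same.

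The rates depend on the SD. With an assumed SD of 0.4 and 30 per group, the same shifts give about 5%, 8% and 11%. The planned primary test is Mann-Whitney, so the t-test figures are an approximation.

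**The case against.** The strongest reply is that nothing in the documents shows an unmasked measurement. The operator is described only as one trained person; the protocol does not say that this person selects or contacts patients or sees the file. Under a combined heading in a single-visit observational study, the entry may simply mean that there is no treatment allocation to conceal. A reader might infer from it that the operator knows each participant's group and that the recordings are therefore biased. The documents support neither step, and this part of the reply stands.

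Much of the mechanism is also limited by design. The index comes from software, the baseline and occlusion periods are each set at 5 minutes, the instruments are calibrated, and one operator removes between-operator variation. Current hs-CRP may not be available during the test. That the operator decides whether to keep or repeat a recording is plausible but is nowhere written. These points stand too, and they are why the risk is modest.

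A reader might also take the 16% or 30% as the study's expected error rate. They are not: no shift of any size is documented. The assumed shifts are about 7% to 25% of the planned difference (20% of 1.51 = 0.302; 0.02/0.302 = 0.07 and 0.075/0.302 = 0.25), so they could not by themselves imitate an effect of that size.

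What the reply does not answer is that the protocol sets aside masking altogether when it could have it almost for nothing. Coding for privacy does not fill the gap, because it does not say who is kept from the group list.

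**Conclusion.** The point holds as a cheap improvement, not as a demonstrated flaw. Declaring blinding not applicable is correct for randomization and incorrect for the outcome assessor, and no other section supplies the safeguard. For the primary outcome, the exposure to bias is confined to how the test is carried out and, by assumption, to any choice to repeat or discard a recording. For skinfolds the measurement itself is manual, but the documents do not say who makes it, and no size is calculated for that outcome.

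The numerical illustration shows only that the comparison would be sensitive to a small systematic shift if the SD really is 0.2. It weakens considerably at a larger SD and says nothing about whether a shift would occur.

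**What to change.** In Study design, item 2, keep the entry not applicable for randomization only, and add a statement on masking along these lines:

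- Whoever performs the EndoPAT tests and the skinfolds, and whoever decides whether a recording is usable, works from the study code alone.
- That person does not see the initial or the current hs-CRP until the measurements are locked.
- The list linking codes to groups is held by a team member who does not measure.

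The study codes already exist, so the cost is a few sentences of protocol text and control of one list. Sample size, visits and equipment do not change. The downside is minor logistics, and it depends on staffing that the documents do not describe. If the operator has to be someone who already knows the groups, the protocol should say so and the report should give it as a limitation.

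### The groups are formed by matching, but the unadjusted RHI comparison ignores it; the adjusted analysis that could use it also conditions on current hs-CRP, and neither is named primary

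*Combined protocol and SAP*

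**What the plan says.** Study population, 1. Recruitment: 30 patients with initially elevated hs-CRP are chosen first and "afterwards matched for age, BMI z-score, and blood pressure with the same number of patients without initially elevated hCRP values". The text mentions no pairs, tolerances or pair identifier, and does not say at which time point the matching values are taken.

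Study design, 3. Statistical methodology: the RHI difference (printed there as THI) "will be evaluated by the Mann Whitney U test". The same sentence adds a second analysis, "Multivariate analysis of variance, taking current hCRP, age, BMI z-score, and systolic blood pressure into account". The two are joined without ranking. No paired or stratified method is planned.

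The power calculation treats the groups as two independent samples of equal size: "we have a power of 0.80 to demonstrate a difference of 20 % between the two groups with 27 patients enrolled in each group".

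Study Objectives: one objective compares RHI by hs-CRP at the initial evaluation. A separate objective relates RHI to current hs-CRP.

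**The concern.** The Mann-Whitney test takes its null variance from two independent samples. Matching on variables that predict RHI makes the groups more alike than independent samples would be. The unpaired variance is then too large, the test rejects less often than its nominal 5%, and the precision bought by matching does not reach that test. In a study of 54 to 60 people this could turn a real, moderate difference into a null result that is read as no association.

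The second analysis includes the matching factors, so it might repair this. It also holds current hs-CRP fixed, and current hs-CRP is a later value of the marker that defines the groups.

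**Working it through.** **Inputs.** From Statistical methodology: mean RHI 1.51, SD 0.2, a 20% difference, power 0.80, 27 per group. From the synopsis: alpha 0.05, with two-sided assumed because sidedness is not stated. From Recruitment: "In total 60 participants will be investigated", that is 30 + 30. The within-pair correlation of RHI, rho, is not in the documents and is assumed to lie between 0 and 0.5.

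**Step 1: the plan's own figure.** For two independent means, n per group = 2 × [SD × (1.960 + 0.842) / d]².
- With d = 0.20 × 1.51 = 0.302: 2 × (0.560 / 0.302)² = 6.9, so 7 per group, not 27. Power at 27 per group is 0.9998.
- With d = 0.10 × 1.51 = 0.151: 2 × (0.560 / 0.151)² = 27.5, so 28 per group. Power at 27 is 0.79.
- The detectable difference at 27 per group is 0.560 × √(2/27) = 0.152, or 10.1% of 1.51.

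The stated sample size therefore corresponds to about a 10% difference, or to 20% with an SD near 0.4. Both give the same standardised effect (0.151 / 0.2 = 0.302 / 0.4 = 0.755). The power comparison below uses d = 0.151. The sample-size mismatch is a separate point.

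**Step 2: effect of ignoring pairs.** The unpaired SE of a mean difference is SD√(2/n). The true SE is SD√(2(1 − rho)/n). Their ratio is √(1 − rho).

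Simulated size and power (20,000 runs per setting, normal data, 27 pairs), and pairs needed for 80% power from 2(1 − rho)(0.560 / 0.151)²:

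| rho | True / unpaired SE | Mann-Whitney size | Mann-Whitney power | Signed-rank power | Pairs for 80% power |
|---|---|---|---|---|---|
| 0 | 1.00 | 0.047 | 0.75 | 0.75 | 28 |
| 0.1 | 0.95 | 0.041 | 0.76 | 0.78 | 25 |
| 0.2 | 0.89 | 0.029 | 0.78 | 0.84 | 23 |
| 0.3 | 0.84 | 0.019 | 0.79 | 0.88 | 20 |
| 0.5 | 0.71 | 0.008 | 0.82 | 0.96 | 14 |

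At rho = 0 the unrounded powers are 0.754 and 0.746, so pairing loses about 1 point. With 30 pairs, Mann-Whitney against signed-rank is 0.80 against 0.83 at rho 0.1 and 0.87 against 0.97 at rho 0.5. At the stated difference of 0.302, power is at least 0.999 for both tests across rho 0 to 0.5.

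**Step 3: group matching.** With 27 per group matched by fifths of one covariate score, Mann-Whitney size is 0.033, 0.021 and 0.008 when the score explains 20%, 30% and 50% of RHI variance. Power is 0.77, 0.78 and 0.81, against 0.86, 0.89 and 0.97 for a model adjusted for the score. The problem is the same as with pairs, but the remedy differs.

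**Step 4: can adjustment recover the precision?** With exact matching on three covariates and 27 pairs, a linear model adjusted for them keeps its size near 0.05. Power for d = 0.151:

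| RHI variance explained | Adjusted model | Paired t | Mann-Whitney |
|---|---|---|---|
| 0.1 | 0.82 | 0.81 | 0.76 |
| 0.2 | 0.86 | 0.85 | 0.78 |
| 0.3 | 0.90 | 0.90 | 0.79 |
| 0.5 | 0.97 | 0.97 | 0.81 |

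It can, provided that the covariates are the matching values.

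**Step 5: adding current hs-CRP.** If current hs-CRP has correlation r with group and explains no further RHI variance, the SE of the group effect grows by 1/√(1 − r²). At an assumed r = 0.5 this is 1/√0.75 = 1.155. In simulation with 20% of RHI variance explained by the matching variables, power falls from 0.86 to 0.73, which is below the unadjusted test's 0.78. The estimate also changes meaning: it becomes the difference by initial hs-CRP among people with equal current hs-CRP.

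**The case against.** A reader might infer that the patients are individually paired and that a signed-rank test is therefore required. The wording leans towards 1:1, but it fits group matching as well, and then there are no pairs to analyse.

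A reader might also infer that a wrong standard error endangers the trial's conclusions. The documents do not support that: the error is in the conservative direction and does not raise the false-positive rate above 5%.

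A third tempting reading is that the benefit of matching is lost altogether. It is not. Matching still balances potential confounders between the groups under an unpaired test, and the planned adjusted analysis already includes age, BMI z-score and systolic pressure.

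The size is uncertain too. With exact matching, rho equals the share of RHI variance explained by the matching variables, and the documents give no such figure. Loose matching, or matching on values from 2006 to 2010, would lower it. At rho 0.1 the power difference is only 2 to 3 points, and at the stated 20% difference it vanishes.

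All of this stands and limits the point. It does not remove it, because the plan does not secure the recovery that the adjusted analysis offers. That analysis conditions on current hs-CRP, does not say whether its covariates are the matching values or visit values, and is not named primary.

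**Conclusion.** The point holds as a conditional loss of efficiency and a gap in specification, not as a threat to validity. The Mann-Whitney test ignores the matching. Its size falls to between 0.041 and 0.008, and its power for a 10% difference is about 2 to 14 points below that of a paired test, for assumed rho between 0.1 and 0.5. At rho = 0 there is nothing to gain.

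These figures rest on an assumed correlation, normal data, SD 0.2, and a 10% difference in place of the stated 20%. The loss of power from adding current hs-CRP rests on an assumed correlation of 0.5 with group and no independent effect on RHI. The change in what the contrast means needs no such assumption.

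**What to change.** State in Recruitment whether matching is 1:1 or by group, with tolerances and the time point of the matching values. In Statistical methodology, name one primary RHI analysis that respects the matching and does not condition on current hs-CRP:

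- **If 1:1:** record a pair identifier at selection. Use the Wilcoxon signed-rank test on within-pair RHI differences, with the Hodges-Lehmann estimate and 95% CI. Add a mixed model with pair as a random effect, so that incomplete pairs still contribute.
- **If by group:** use a linear model of RHI on initial hs-CRP group, adjusted for the matching values of age, BMI z-score and blood pressure.

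Keep the model with current hs-CRP for the separate objective on current hs-CRP.

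The cost is a few sentences and, if 1:1, one data column, which may be impossible to reconstruct later. Incomplete pairs drop out of the signed-rank test, and about 1 to 2 points of power are lost if the matching proves uninformative.
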